Recent randomised controlled trial (RCT) data has demonstrated that pharmacological therapy with antipsychotics has limited success in managing symptoms of delirium in palliative care patients once they occur. Hence, we believe the urgent priority in advanced cancer should be on delirium prevention, given the wide reaching improvements in health outcomes that could be achieved. Delirium prevention strategies include complex multicomponent non-pharmacological interventions; however the inclusion of cognitive and exercise based strategies make adherence unachievable for many advanced cancer patients suffering fatigue and functional decline.

Alternative strategies for preventing delirium in advanced cancer are therefore needed, with robust evaluation via RCTs. A supplemental pharmacological approach with an acceptable adverse effect profile is an attractive alternative; and melatonin shows particular promise. Clinical and laboratory data identify low melatonin levels and circadian desynchrony in delirium, and 3 RCTs have demonstrated support for melatonin as a safe preventative agent in the hospitalised elderly. The team completed a phase II RCT (n=30) and established feasibility of trial methods and demonstrated potential for increase in delirium-free days and lower delirium incidence rate.

Study design:

A prospective, randomised, double-blind, placebo-controlled parallel-arm, multicentre phase III trial of oral prolonged release melatonin 2mg versus placebo taken each night during inpatient oncology or palliative care admission.

Objectives:

The **primary objective** is to determine if oral prolonged release melatonin compared to placebo can increase the number of delirium-free days during hospitalisation for advanced cancer patients.

Secondary objectives are to determine if oral prolonged release melatonin can:

- 1. reduce delirium severity and duration for those who develop a delirium episode;
- 2. reduce delirium incidence;
- 3. cause adverse effects, in particular sedation;
- 4. positively influence adverse events associated with delirium episodes, including:

- i. length of hospital stay and inpatient resource utilisation;
- ii. benzodiazepine and antipsychotic use (delirium or non-delirium indication);
- iii. in-hospital complications (pressure areas, falls, thromboembolism, pneumonia, functional decline);
- iv. days spent in coma and survival;
- v. Patient and family distress;
- 5. provide other symptom benefits in the form of improved sleep quality.

Treatment schedule: Oral melatonin prolonged release (2mg) or placebo taken at 2000 hours. Intervention will be commenced within 48 hours of admission and continued until delirium occurrence, discharge or three weeks if patient remains in hospital (e.g. while awaiting long-term care placement) after any acute medical issues imparting a delirium risk have been resolved.

Assessments: Delirium Rating Scale – Revised – 98 (DRS-R-98);¹ Nursing Delirium Screening Scale (NuDESC);² Delirium Etiology Checklist (DEC);³ Short Blessed Test (SBT);⁴ Insomnia Severity Index (ISI); ⁵ Charlson Comorbidity Index;⁶ Richmond Agitation-Sedation Scale (RASS);⁷; EQ-5D-5L⁸, Australian Karnofsky Performance Status (AKPS);⁹ 15ml blood will be drawn at baseline and any delirium events.

Definition of response: no delirium defined as DR-R-98 ¹ (total score <17.75) for entire admission.

Primary endpoint: Delirium-free days (which occur before delirium onset for any participant who develops delirium).

Analysis: Intention-to-treat analysis will be used for all statistical comparisons. For the primary outcome, comparisons between groups for delirium-free days, with adjustment to the length of stay and other potential covariates using a general linear model approach will be undertaken. For the secondary outcomes, time-to-event analysis, such as survival analysis will be used to determine differences in time to first episode of delirium. Delirium precipitants, which occur at variable times and for different durations during the study period are time-dependent covariates and proportional logistic regression modelling will be used. The incidence rate of delirium, will also be calculated and compared between the treatment and control groups. Two planned interim analyses will be conducted independently and reviewed by the independent data and safety monitoring committee after about 33% and 66% of patients have been enrolled. The primary outcome and adverse events will be compared between groups with p<0.001 required as the threshold of stopping the trial for significant evidence of benefit or harm in either one of the treatment arms.

Economic analysis:

The within-study cost-effectiveness will estimate incremental costs, effects and net benefit of prolonged release melatonin relative to placebo from participant level data collected over 21 days of follow up (survival to 21 days or death whichever is shorter) for the following:

• resource use:

[figure not shown]
- bed days spent in hospital for inpatient admissions (index admission and readmissions);
- o within-hospital resource use; health care professional time (particularly nursing time), diagnostic & investigational services;
- professional community support utilised at home if discharged from hospital, including general practitioner and palliative care service visits,
- o concomitant medication use; and

effects:

- o days of survival without delirium,
- o toxicity,
- o adverse events,
- o health related quality of life

Bootstrapping of patient costs and effects data will be used to model decision - making uncertainty related to the net benefit and value for money of prolonged release melatonin relative to placebo.

Study diagram

*Standardardised non-pharmacological prevention protocol in both arms: for reducing delirium risk (targeting sleep preservation, mobility, orientation and sensory deficit minimisation) and to standardise light exposure at night.

Table of study measures

	Eligibility	Baseline	Daily	Delirium occurrence	Discharge	Follow-up [#]
Investigations						
Liver function	*			*		
Electrolytes	*			*		
Full blood count	*			*		
Measures						
Medical file review						
Demographics	*					
Diagnosis	*					
Con meds	*	*	*	*	*	*
Prn medications		*	*			
Specific medications: Anticholinergics, corticosteroid and benzodiazepines CYP1A2 inhibitors (quinolones, carbamazepine, rifampicin, fluvoxamine) Warfarin Vital signs Admission data Preventative care non-pharm		* * *	*	*		*
measures						
Survival					*	*
Falls			*		*	*
Pressure areas			*		*	*
Pneumonia			*		*	*
Length of stay					*	
Health services utilisation					*	*
In hospital			*		*	
resource utilisation						
Patient measures						
Vision	*					
Hearing	*					
AKPS	*	*		*	*	*
Short Blessed Test		*			*	
Insomnia Severity Index		*	Every five days			at.
Quality of life (EQ-		*			*	*

	Eligibility	Baseline	Daily	Delirium occurrence	Discharge	Follow-up [#]
5D-5L)						
Medical assessment	*		*			
Delirium Experience					* (only if delirium	* (only if delirium
Questionnaire					occurred)	occurred)
Clinician assessed						
Toxicity		*	*	*		*
Charlson		*				
Comorbidity Index						

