5.0 INTERVENTIONS

5.1 Study medication

Arm 1: Oral melatonin prolonged release 2mg (Neurim Pharmaceuticals Ltd) taken at 2000 +/-hours. Intervention will be commenced within 48 hours of admission and continued until delirium occurrence, discharge or for a maximum of three weeks if patient remains in hospital (e.g. while awaiting long-term care placement) after any acute medical issues imparting a delirium risk have been resolved.

Arm 2: Oral placebo tablet containing identical ingredients except the active ingredient melatonin

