5.12 Cessation of study drug

- Participant request
- Unacceptable side effects from study medications (defined by National Cancer Institute Common Criteria for Adverse Events; CTCAE version 4.0).
- Participants who in the opinion of the investigator are not well enough to continue the study (Specific reasons for withdrawal need to be documented in the Case Report Form)
- Treatment deemed ineffective by treating clinician, who wishes to use alternative therapy.
- Occurrence of delirium (completion of study)
- Can no longer swallow
- Discharge from Hospital (completion of study)
- The participant withdraws their consent, with or without consent to use already collected data.
- It is inappropriate to continue the study medication for whatever reason

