5.13 Post study treatments

All participants will be followed by their clinician for continuing care, irrespective of the point at which they exit the study.

Treatment continuation: Melatonin will only be available for currently approved indications (primary insomnia) if the participants meets that indication, after study completion (on discharge). The treatment available to reduce delirium risk after discharge will be determined by the treating clinician, and can include individualised strategies to reduce risk of delirium including regular exercise as tolerated, maintaining vision and hearing or using aids, regular reorientation and non-medication methods to improve sleep (quiet room, relaxation for example).

In all study participants, regardless of above choices, secondary outcomes and collection of data for will occur until the end of the inpatient admission after randomization, unless consent is withdrawn

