7.8 Sedation

Sedation will be rated daily by observation using the Richmond Agitation-Sedation Scale (RASS-Pal). This has modified the intensity of verbal or physical stimuli required to avoid additional discomfort in the palliative population, and has good correlation with the original RASS (interclass correlation coefficient 0.83 – 0.98). It is a 10-point scale using observation, verbal stimulation, and physical stimulation, the last used only to assess the two (out of five) deepest levels of sedation. It has been selected because it gives clear descriptors for assigning scores, differentiates between different potency of stimulation (verbal versus physical), includes agitation and sedation, and also looks at constructs related to delirium (inattention as measured duration of eye contact). It will also assess days in coma defined as RASS-Pal score of -4 or -5. ⁵⁹ Other adverse effects will be assessed using the National Cancer Institute Common Terminology Criteria. ⁶⁰

7.8.1 Benzodiazepine and antipsychotic use:

Regular use and administration of 'as required' doses of all benzodiazepine and antipsychotics will be recorded daily, including the clinical indication. This will capture whether there is a reduced need for nocturnal sedation due to concurrent melatonin use and benzodiazepines/antipsychotic administration for delirium symptoms.

7.8.2 Delirium risk factors:

These risk factors will be recorded at baseline: age (over 65 and over 80 years are categories of interest), prior cognitive impairment defined as defined as SBT score >4, visual impairment, presence of infection, and use of physical restraint ²⁶. Risk factors which have uncertain/contradictory evidence will also be collected to take the science forward for future work: cerebral primary or secondary cancer, use of benzodiazepine use (oral diazepam equivalents), corticosteroids (oral dexamethasone equivalents), opioids (oral morphine equivalents), anticholinergic load (Clinician rated anticholinergic scale ⁶⁴), hearing impairment, comorbidities (Charlson Comorbidity Index > 3 ⁶ diagnosis of depression from medical record, presence of indwelling bladder catheter, multiple medications (number of medications at baseline), and high blood urea to creatinine ratio (above 18). ^{26,65} The number of room /bed changes during the admission will be recorded ²⁶.

7.8.3 Delirium precipitating factors:

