9.3.1 Time period for assessing AE's and SAE's

At each visit, the participants are encouraged to mention any problems since the last visit. In addition, the following standard questions should be asked;

- 1. Have you had any medical problems since the last visit or study assessment?
- 2. Have you started any new medications, other than given to you in this study, since the last visit or assessment?

For all randomised participants all AE's, irrespective of causality, will be assessed and recorded as per the standard operating procedures. The time period includes the time from randomisation, the inpatient treatment period and the 4 week extension phase (by telephone).

For patients who meet the eligibility criteria and then do not proceed to randomisation, any AE's detected during that window of time, should be reported. If an AE is the reason that a person does not proceed to randomisation, this should be recorded within the CRF, adverse event report and in the clinical record, irrespective of causality or seriousness.

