9.3.2 National Cancer Institute, Common Terminology Criteria for Adverse Events.V4.0

These criteria ⁷⁰ have been used to determine adverse events likely to occur during the study period and will be used to determine adverse event reporting and study progress. Criteria specific to the expected events know to be associated with melatonin have been listed below. This is administered by study staff

Symptoms will be identified during each visit using criteria established by the National Cancer Institute, and will be graded accordingly.

Specifically, for this study, the symptoms of interest will be;

[figure not shown]
- Sedation
- Dizziness
- Seizure
- Agitation
- Anxiety
- Increased INR

• Depression

A grade of 3 (that has not responded to symptomatic treatment instituted by the treating physician according to local protocols) or 4 will activate cessation of study intervention and an adverse event report.

All adverse events will be collated by the project officer, and reported to the executive committee on a monthly basis. Adverse event rates will form part of the Key Performance Indicators for the study and will be reported on a regular basis to the Trial Steering Committee and the ethical review boards of the participating sites.

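### The sedation question is answered on a mix of on-drug and post-delirium off-drug days, because no on-drug toxicity summary stands beside the intention-to-treat rule

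*Protocol*

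**What the plan says.** **The question.** Secondary objective 3 (Protocol, Trial summary and 2.2.2) asks whether melatonin can "cause adverse effects, in particular sedation".

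**When drug stops.** Section 5.1 has treatment "continued until delirium occurrence, discharge or for a maximum of three weeks". Section 5.12 lists among the reasons for cessation "Occurrence of delirium (completion of study").

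**When data stop.** Section 5.13 says that, whatever the later treatment choices, "secondary outcomes and collection of data for will occur until the end of the inpatient admission after randomization". The table in 8.1 schedules toxicity at baseline, daily, at delirium occurrence and in follow-up. It schedules the sedation scale at baseline and daily. For adverse events, 9.3.1 says: "The time period includes the time from randomisation, the inpatient treatment period and the 4 week extension phase (by telephone"), irrespective of causality. The table footnote in 8.1, and 8.12, put follow-up at up to 21 days after the last dose.

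**What is measured.** Section 9.3.2 says: "Symptoms will be identified during each visit using criteria established by the National Cancer Institute, and will be graded accordingly". Its symptoms of interest include sedation, agitation and anxiety. The sedation scale (RASS-Pal, 7.8) "also looks at constructs related to delirium (inattention as measured duration of eye contact"). Section 6.2 also uses it to count coma days, which it expects in severe irreversible delirium before death.

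**How it is analysed.** The Trial summary and 11.2 both say: "Intention-to-treat analysis will be used for all statistical comparisons". Section 11.3 says only that adverse-event incidence will be calculated and reported. Sections 9.7 and 11.6 have adverse events compared between arms at two interim looks, with p<0.001 as the stopping threshold.

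**The concern.** Delirium ends drug exposure and itself produces symptoms on the toxicity list. Section 1.1 names agitation as a delirium symptom. Benzodiazepines or antipsychotics given for delirium may sedate as well. A participant who becomes delirious moves from on-drug days to off-drug days with a high chance of being rated sedated or agitated, and the toxicity data continue through both.

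A comparison over all rated days therefore mixes two effects: what the drug does to alertness, and what it does to the number of delirium days. If melatonin works, these pull in opposite directions, and the better it prevents delirium, the harder its own sedation is to see. The trial could report no excess sedation in frail patients, on the one adverse effect that its objectives name, when an excess exists.

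**Working it through.** The protocol gives no sedation rate, toxicity effect size or toxicity power, so there is no stated figure to reproduce. What follows is illustration.

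**Inputs from the protocol (1.2, 1.3 and 11.5)**
- Pilot mean delirium-free days over three weeks: 20.0 melatonin, 17.9 placebo.
- Pilot delirium cases: 1 melatonin, 4 placebo. The pilot is described as n=30, but the incidence is given out of 20, so no arm percentages are taken from it.
- Planned size: 110 per arm.

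**Assumptions**
- Days before onset are on drug and days after it are off drug. All 21 days are rated, so earlier discharge is ignored.
- Sedation on background days: s = 10% (range 5% to 20%).
- True on-drug excess: d = 5 points.
- Sedation on days after delirium onset: q = 50% (range 30% to 70%).

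**Off-drug share of days**
- Melatonin: (21 - 20.0)/21 = 4.8%
- Placebo: (21 - 17.9)/21 = 14.8%

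Placebo carries about three times the post-onset days (3.1 against 1.0).

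**All-days sedation rate** = (1 - off-drug share) x on-drug rate + off-drug share x q
- Melatonin: 0.952 x 0.15 + 0.048 x 0.50 = 16.7%
- Placebo: 0.852 x 0.10 + 0.148 x 0.50 = 15.9%
- Observed excess: about 0.8 points, against a true 5.0. Using on-drug days alone returns 5.0.

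**Range.** With s from 5% to 20% and q from 30% to 70%, the true 5-point excess reads as -1.7 to +3.8 points.

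**Delirium equally common in both arms.** With 14.8% off-drug days in each arm, the post-onset terms cancel and the excess is 0.852 x 5 = 4.3 points.

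**Per participant.** Assume true sedation of 10% against 20% (power 55% at 110 per arm), 27% delirium on placebo (within the 20% to 45% in section 1.1), and half of delirious participants logged as sedated or agitated.
- Delirium risk ratio 0.5: placebo 1 - 0.90 x (1 - 0.135) = 22.2%; melatonin 1 - 0.80 x (1 - 0.0675) = 25.4%. The difference is about 3.2 points and power falls to 8%.
- Delirium risk ratio 1: melatonin 1 - 0.80 x 0.865 = 30.8%. The difference is 8.6 points and power is 31%.

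**The case against.** **Intention-to-treat sets the arm, not the window.** This is right. A reader might infer that the rule itself pulls in off-drug days, but those days come from the collection windows in 5.13, 8.1 and 9.3.1. An on-drug summary by randomised arm would not breach the rule. What stands is that no on-drug summary is stated, so the plan followed literally uses all the data.

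**This belongs in the SAP, and 11.3 only reports adverse events.** A missing safety set alone would be no finding, and the SAP was not available for this review. But the protocol itself fixes one rule for all comparisons and an event window that outlasts the drug, and it compares adverse events between arms at the interim looks. Objective 3 can be answered only by comparing arms.

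**Filters exist.** Section 9.2.1 exempts symptoms of the disorder under study from adverse-event reporting unless they are worse than expected, and 9.3 has each event graded for causality. So the documents do not support the reading that every delirium symptom is booked as drug toxicity. Neither filter touches the daily RASS-Pal ratings, which carry no attribution.

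**Post-onset sedation rating is not fully settled.** Section 5.12 calls delirium completion of study, and 8.10 places the exit assessment at treatment cessation. Against that, 5.13 continues secondary outcomes to the end of admission, and coma days from delirium (6.2) can be counted only if ratings continue. Continuation is the better reading.

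**Follow-up as the main source of dilution.** A reader might weight the follow-up days like inpatient days and read a true ratio of 2 as (42 + 21)/42 = 1.5 for 21 treatment days. The schedule does not support this: RASS-Pal is not scheduled in follow-up, and contact is a weekly call. By visits, 21 daily visits plus 3 calls give (42 + 3)/24 = 1.88, and 7 visits plus 3 calls give (14 + 3)/10 = 1.70.

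**An on-drug analysis has its own bias.** This also stands. Its window ends at delirium, which treatment may affect. The DRS-R-98 sleep-wake item scores daytime drowsiness, so drug sedation could push a participant towards the cut-off and out of the window. This argues against replacing the intention-to-treat table, not against adding a second one.

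**Conclusion.** The point holds as a cheap and worthwhile improvement to the analysis plan. As written, the sedation question is answered on a mixture of on-drug days and off-drug days after delirium, with nothing stated to separate them.

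The size is uncertain because every sedation rate above is assumed. In the illustration a true 5-point excess shrinks to about 0.8 points if melatonin lowers delirium as the pilot suggests, and to about 4.3 points if it does not.

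A reader might infer that the bias certainly loads onto placebo. The documents do not support that. It follows only if melatonin prevents delirium, the trial's own evidence is 4 against 1 pilot cases, and the n=452 hip-fracture trial described in 1.3 saw no effect on incidence. Without prevention there is mild dilution and no imbalance between arms.

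**What to change.** 1. Keep the whole-window, intention-to-treat toxicity comparison.
2. Add to 11.3, and to the interim adverse-event reports, wording such as: RASS-Pal sedation and the symptoms of interest will also be summarised by arm among participants who took at least one dose, per on-drug day, from first dose to a fixed short interval after the last dose, taking the baseline grade into account. Ratings at or after delirium onset will be tabulated separately.
3. State that this summary accompanies the intention-to-treat table and does not replace it, because its window ends at a post-randomisation event that treatment or sedation may influence.
4. Reconcile the 4-week telephone phase in 9.3.1 with the 21 days in 8.1 and 8.12, so that the whole-window table has one defined end.

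The cost is a few sentences and one table. Dose administration (5.5), baseline toxicity (8.1) and time of delirium occurrence (7.7.1) are already recorded. No treatment or assessment changes.

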13.2	QUALITY CONTROL	60
13	3.2.1 Training procedures:	60
13	3.2.2 Blood collection	60
13	3.2.3 Peer review and site visits	60
13	3.2.4 Pharmacy training	61
13	3.2.5 Monitoring visits	61
14.0 F	REFERENCES	62
15.0 A	APPENDICES	67
15.1	Assessment tools	67
15.2	PROTOCOL AMENDMENTS	79
15.3	AMENDMENT NUMBER - 1	79
15.4	INFORMATION SHEETS AND CONSENT FORMS	80
15.5	PRODUCT INFORMATION AND INVESTIGATOR BROCHLIRE	80

LIST OF ABBREVIATIONS

μg	microgram
AE	Adverse Event
AIN	Assistants in Nursing.
AKPS	Australia – modified Karnofsky Performance Status
AMH	Australian Medicines Handbook
BD	Twice daily
BPI	Brief Pain Inventory
ВТ	Breakthrough
CADSS	Clinician Assessed Dissociative States Scale
CAM	Confusion Assessment Method
CIRS	Cumulative Illness Rating Scale
CRF	Case Report Forms
DRG	Diagnosis Related Group
DRS	Delirium Rating Scale
DSM III R	Diagnostic and Statistical Manual of Mental Disorders. Third edition – revised
DSM IV R	Diagnostic and Statistical Manual of Mental Disorders. Fourth edition - revised
ECOG	Eastern Co-operative Oncology Group
EORTC-QLQ- C	European organization for Research and Treatment of Cancer- Quality of Life Questionnaire- core
EPS	extrapyramidal side effects
ESRS	Extrapyramidal Symptom Rating Scale
FACIT-PAL	Palliative care quality of life instrument used in this protocol
FDA	Food and Drug Administration
HIC	Health insurance commission
HREC	Human Research Ethics Committee
ICH GCP	International Conference on Harmonisation, Good Clinical Practice
ICU	Intensive Care Unit
ID	Identification number
IQCODE	Short informant Questionnaire on Cognitive Decline in the Elderly
IVI	Intra Venous Injection
kg	Kilogram

LANSS	Leeds Assessment of Neuropathic Symptoms and Signs
МА	Medicare Australia
MDAS	Memorial Delirium Assessment Scale
mg	milligram
ml	millilitre
N/saline	Normal saline
NCI	National Cancer Institute
NMDA	N-methyl-D-aspartate
NRS	Numeric Rating Scale
NSAID	Non steroidal anti-inflammatory drug
NuDesc	Nursing Delirium Screening Scale
O2	Oxygen
PaCCSC	Palliative Care Clinical Studies Collaborative
PBS	Pharmaceutical Benefits Scheme
PS	Performance status
QALY	Quality adjusted life years
QOL	Quality of life
QT Interval	The relationship between two conduction points on an electrocardiograph (ECG)
RASS	Richmond Agitation Sedation Scale
RCT	Randomised controlled trial
SAE	Serious Adverse Event
SC	Subcutaneous
SCN	suprachiasmatic nucleus
SOP	Standard Operating Procedure
TGA	Therapeutic Goods Administration
VAS	Visual Analogue Scale

